We recognize that there is risk for inherent bias within our study as patients are unable to be completely blinded to type of treatment he/she receives because each treatment procedure is distinctly different. Risk of selection bias is minimized by use of a randomized allocation schedule. Risk of influence on the patient when completing clinical outcome scales will be negated as the research team member administering the clinical outcome tools at 3, 6, and 12 months post-treatment will be blinded to group allocation.

ClinicalTrials.gov

As this study meets the FDAAA 801 definition of an “Applicable Clinical Trial” based on a drug and biologic, it is required that the study be registered on ClinicalTrials.gov. The Principal Investigator will register and activate the study account prior to enrollment, and all results will be entered upon study completion, followings statistical analysis, per the Results Database Guidelines.

2.5 – Statistical Analysis

Aim 1: Change in mean KOOS subscale scores over time based on treatment group

Total scores will be calculated for each patient using the KOOS subscales. The validated analysis guidelines for the KOOS instrument will be used. Patient’s total scores will be compared at baseline, 3 months, 6 months, and 12 months post treatment and compared by treatment group.

The statistical method that will be used is a Repeated Measures ANOVA (RM-ANOVA). This statistical strategy will allow us to control for the correlation in each individual’s measurements over time. The use of the standardized scales ensures that the outcome variable will be normally distributed, which will meet the underlying assumptions of the RM-ANOVA analysis. We will use the KOOS subscale score as the dependent variable, and the treatment assignment as the independent variable. If the distribution of gender is unequal across treatment groups after randomization, this statistical method will allow us to control for gender because changes in score will differ by gender. We will also be able to control for clinically meaningful variables such as patient age or BMI if there are differences in these variables between the two treatment groups at baseline.

Aim 2a: Change in mean NPRS score over time based on treatment group

Total scores will be calculated for each patient using the NPRS. The NPRS instrument will be processed using the tool’s validated analysis guidelines. Patient’s total scores will be compared at baseline, 3 months, 6 months, and 12 months post treatment and compared by treatment group.

The statistical method that will be used is a RM-ANOVA. This statistical strategy will allow us to control for the correlation in each individual’s measurements over time. The use of the standardized scales ensures that the outcome variable will be normally distributed, which will meet the underlying assumptions of the RM-ANOVA analysis. We will use the NPRS as the dependent variable, and the treatment assignment as the independent variable. If the distribution of gender is unequal across treatment groups after randomization, this statistical method will allow us to control for gender

because changes in score will differ by gender. We will also be able to control for clinically meaningful variables such as patient age or BMI if there are differences in these variables between the two treatment groups at baseline.

Aim 2b: Change in mean PROMIS – Global Health score based on treatment group

Total scores will be calculated for each patient using the PROM Global Health scale (short form, version 1.1). The PROMIS global health instrument will be processed using the tool's validated analysis guidelines. Patient's total scores will be compared at baseline, 3 months, 6 months, and 12 months post treatment and compared by treatment group.

The statistical method that will be used is a RM-ANOVA. This statistical strategy will allow us to control for the correlation in each individual's measurements over time. The use of the standardized scales ensures that the outcome variable will be normally distributed, which will meet the underlying assumptions of the RM-ANOVA analysis. We will use the PROMIS global health scale as the dependent variable, and the treatment assignment as the independent variable. If the distribution of gender is unequal across treatment groups after randomization, this statistical method will allow us to control for gender because changes in score will differ by gender. We will also be able to control for clinically meaningful variables such as patient age or BMI if there are differences in these variables between the two treatment groups at baseline.

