The purpose of this study is to determine the clinical response to autologous BMAC and PRP injections for KOA with respect to pain, function, and quality of life at up to 1 year following the intervention. This is a prospective randomized controlled trial with the following aims:

Specific Aim 1: To determine if BMAC and PRP treatment of KOA improves Knee injury and Osteoarthritis Outcome Score (KOOS) subscales for patients measuring pain, function, and quality of life at 3 months, 6 months, and 12 months post treatment compared to Gel-One® hyaluronate injections and relative to baseline.

A change in 10 points has been suggested³⁶ and utilized³⁷ to demonstrate a minimal clinically important difference (i.e., decline or improvement) in each KOOS subscale. In this study, we expect to see a mean improvement of greater than 10 points at 3 months post treatment in the patients receiving BMAC and PRP injections as well as those receiving the Gel-One® hyaluronate injection. However, we expect to see greater improvement in favor of the group receiving the BMAC and PRP treatment at 6 months and 12 months post treatment.

Specific Aim 2a: To determine if BMAC and PRP treatment of KOA improves pain scores measured by the Numeric Pain Rating Scale (NPRS) at 3 months, 6 months, and 12 months post treatment compared to Gel-One® hyaluronate injections and relative to baseline.

Specific Aim 2b: To determine if BMAC and PRP treatment of KOA improves Patient Reported Outcome Measurement Information System (PROMIS) Global Health scores (short form, version 1.1) at 3 months, 6 months, and 12 months post treatment compared to Gel-One® hyaluronate injections and relative to baseline.

2.0 – METHODS

2.1 – Study Population

The study population will consist of patients presenting to McConnell Spine, Sport, and Joint Physicians, which is focused on conservative, non-surgical solutions for orthopedic issues. The clinic is located in a diverse and large geographic area.

All participating patients will be patients of the McConnell Spine, Sport, and Joint Physicians. Patients participating in the study may be patients of the study physician, referred from an outside practice to the

study physician, or referred from other physicians of the McConnell Spine, Sport, and Joint Physicians to the study physician.

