- 14) Unable to be prescribed stable dose of NSAIDs and/or tramadol based on medical history as ad lib use of OTC analgesics will be allowed in both groups after treatment
- 15) Current cigarette smoker
- 16) Unable to give informed consent
- 17) Non-English speaking

2.2 – Hypotheses

Hypothesis 1: We hypothesize that patients that are treated with BMAC and PRP will have improved KOOS subscale scores at 6 months and 12 months post treatment compared to patients treated with Gel-One® hyaluronate injections and relative to baseline. We hypothesize that both patients treated with BMAC and PRP and patients treated with Gel-One® will have improved KOOS subscale scores at 3 months post treatment relative to baseline.

A sample size of 30 total patients undergoing the treatment intervention has been established based on the power calculation ($\alpha = 0.05$, $\beta = 0.20$) of a previous study comparing allogeneic bone marrow MSCs to hyaluronic acid in 30 patients with knee osteoarthritis³⁰ and a preceding pilot study.³⁸ The primary outcome tool used in the study by Vega et al. has been demonstrated to have similar effect sizes at 6 and 12 months and similar smallest detectable differences compared to the KOOS scale in two different populations with knee-related deficits.^{39,40} A post-hoc power analysis will be completed, if necessary, to evaluate current findings and potentially plan for future studies with this specific study population.

Hypothesis 2a: We hypothesize that patients that are treated with BMAC and PRP will have improved NPRS scores at 3 months, 6 months, and 12 months post treatment compared to patients treated with Gel-One® hyaluronate injections and relative to baseline.

Hypothesis 2b: We hypothesize that patients that are treated with BMAC and PRP will have improved PROMIS Global Health scores at 3 months, 6 months, and 12 months post treatment compared to patients treated with Gel-One® hyaluronate injections and relative to baseline.

2.3 – Study Variables & Outcomes of Interest

Treatment Groups:

- N = 30 patients that will undergo treatment
- Group A: BMAC and PRP injections to target knee (n=15)
- Group B: Gel-One® hyaluronate injection to target knee (n=15)

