The following data points will be collected for patients who choose to participate in the study at McConnell Spine, Sport, and Joint Center (see Table 1). Patient data will be collected via the electronic medical record at the study physician's practice, as well as by means of study specific data collection forms (see Appendices). Only the study staff will have access to the paper data collection forms and the Research Electronic Data Capture (REDCap) database created solely for use in this study. Exported REDCap patient data will be de-identified upon study completion, prior to statistical analysis using SAS 9.4 (SAS Institute Inc., Cary, NC, USA).

Demographics:

- Age, gender, and body mass index (BMI)

Relevant clinical information or past medical history:

- Relevant past medical history related to the involved knee including previous surgical procedures, previous intraarticular injections, other treatments, and course of knee pain
- Kellgren-Lawrence grade of KOA via standing radiograph of the target knee
- Platelet count via complete blood count (Group A only)

Other relevant therapies received following the study treatment:

- Therapies received for the target knee including use of over the counter medications (i.e., Advil, Motrin, or Tylenol), prescription anti-inflammatories or NSAIDs (i.e., Mobic, Naprosyn, Celebrex, or Voltaren), narcotics (i.e., Tramadol, Percocet, Vicodin, or others), or physical therapy

Primary outcome measures:

- Change in KOOS subscale scores which will objectively measure pain, function, and quality of life indicators at 3 months, 6 months and 12 months post treatment (see appendix 4.1 for KOOS scale)

Mean values for the KOOS subscales have been studied in a population-based sample (i.e., not specific to whether those surveyed actually had knee complaints).⁴¹ The population-based sample of subscale scores (i.e., range of 0-100 with a score of 100 representing the best possible score) in the approximate age group of this study ranged from 61 to 89.5, which also varies by gender.⁴¹ A change in 10 points has been suggested³⁶ and utilized³⁷ to demonstrate a minimal clinically important difference (i.e., decline or improvement) in each KOOS subscale.

Secondary outcomes measures:

- Change in pain scores as measured by the NPRS at 3 months, 6 months, and 12 months post treatment (see appendix 4.2 for NPRS scale)

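### Post-hoc power cannot show which KOOS differences the data exclude; report the between-arm difference with its 95% CI instead

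*Combined protocol and SAP*

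**What the plan says.** The sample-size paragraph under Hypothesis 1 in section 2.2 ends with this sentence: "A post-hoc power analysis will be completed, if necessary, to evaluate current findings and potentially plan for future studies". The analysis is conditional, with no stated trigger. It has two purposes: judging this trial's results, and planning later ones. The plan does not say whether the effect entered would be the observed one or a pre-set one.

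Section 2.1 fixes 30 treated patients, 15 per group. Hypothesis 1 sets the comparison between arms at two visits: patients given BMAC and PRP "will have improved KOOS subscale scores at 6 months and 12 months post treatment compared to patients treated with" Gel-One. Aim 1 in section 1.2 and the primary outcome in section 2.3 also include 3 months: "Change in KOOS subscale scores which will objectively measure pain, function, and quality of life indicators at 3 months, 6 months and 12 months".

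Sections 1.2 and 2.3 give a change of 10 points as the figure "to demonstrate a minimal clinically important difference (i.e., decline or improvement) in each KOOS subscale". Neither section calls it a margin between arms.

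Section 2.5 (Aim 1) specifies a repeated-measures ANOVA: "We will use the KOOS subscale score as the dependent variable, and the treatment assignment as the independent variable". Scores are compared by group at baseline, 3, 6 and 12 months. Section 2.5 names no estimated between-arm difference, no confidence interval and no contrast at a given visit, and no other section supplies one.

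**The concern.** With 15 patients per arm, a non-significant KOOS comparison is a realistic outcome. Such a result can mean two different things. The data may rule out a clinically relevant advantage for BMAC and PRP, or they may be compatible with one. The only tool the plan names for judging the findings beyond the test itself is post-hoc power, which cannot tell these two cases apart. Without an interval fixed in advance, a non-significant result is more easily reported as showing no difference, or excused as merely underpowered.

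**Working it through.** **Inputs.** From the documents: 15 per arm (sections 2.1 and 2.3), alpha 0.05 (section 2.2) and 10 KOOS points as a minimal important change (sections 1.2 and 2.3). Assumed: a two-sided test (sidedness is not stated), no losses, a two-group comparison of change from baseline at one visit with 28 df, and the SD of change, since the documents give no KOOS SD. Ten points serves here only as a yardstick for the difference between arms.

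**The plan's own figure.** The 30 patients rest on an earlier study's calculation at alpha 0.05 and beta 0.20. No KOOS difference or SD is stated, so that figure cannot be reproduced. The present point does not need it.

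**Form 1: power from the observed effect.** The observed standardised effect is d = t(1-p/2, 28) x sqrt(2/15), so the noncentrality d x sqrt(15/2) is the observed t itself. At fixed n, power then depends on p and nothing else:

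| p | observed t | power |
|---|---|---|
| 0.05 | 2.05 | 51% |
| 0.10 | 1.70 | 38% |
| 0.20 | 1.31 | 25% |
| 0.50 | 0.68 | 10% |

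At p = 0.30 it is 17.5% whatever the SD. With an SD of 8 the difference is 3.1 points, CI -2.9 to 9.1, which excludes 10. With an SD of 15 it is 5.8 points, CI -5.4 to 17.0, which does not. The power figure is the same for both.

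**Form 2: power for a pre-set 10 points with the observed SD.** Take an SD of change of 10.

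- SE = 10 x sqrt(2/15) = 3.65.
- CI half-width = t(0.975, 28) x SE = 2.048 x 3.65 = 7.48.
- Noncentrality for 10 points = 10/3.65 = 2.74, which gives power 75%.

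| SD of change | observed advantage | p | 95% CI | 10 points excluded? | power for 10 points |
|---|---|---|---|---|---|
| 10 | +2 | 0.59 | -5.5 to 9.5 | yes | 75% |
| 10 | +5 | 0.18 | -2.5 to 12.5 | no | 75% |
| 15 | -3 | 0.59 | -14.2 to 8.2 | yes | 42% |
| 15 | +5 | 0.37 | -6.2 to 16.2 | no | 42% |

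The observed difference does not enter this calculation, so within each pair the power is identical while the conclusions differ. At an SD of change of 10, a non-significant result excludes a 10-point advantage only if the observed difference is below 10 - 7.48 = 2.52 points. Only the interval shows on which side of that line the result falls.

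**The case against.** **Post-hoc power is not empty.** The plan does not say which form it intends. At fixed n, power for a pre-set difference with the observed SD maps one-to-one to the CI half-width: above, 75% goes with 7.5 points and 42% with 11.2. It therefore informs on precision. This stands, and a reader who infers that post-hoc power is uninformative in every form goes too far. It still says nothing about where the estimate lies, so it cannot show what has been excluded.

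**The sentence is conditional and serves a second, legitimate purpose.** This also stands. Planning a later study from the observed SD is good practice. Nothing in the documents says that post-hoc power would excuse or override a result. The harm is a possible misreading at the reporting stage. No test, data item or stopping decision is affected.

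**Ten points is given as a change, not as a difference between arms.** Correct. Any rule that classifies results against 10 points needs a decision by the sponsor and must stay optional. The core repair does not depend on it.

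**A reader might infer that the stated 80% power is wrong or that the trial is too small.** The documents do not support this. The figure is carried over from an earlier trial of another cell product with another outcome tool, and from a pilot. The link to KOOS is qualitative: "similar effect sizes at 6 and 12 months and similar smallest detectable differences compared to the KOOS scale in two different populations". Without a stated KOOS difference or SD the 80% can be neither confirmed nor refuted.

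**Conclusion.** The concern holds for one of the two stated purposes, judging the trial's own findings. From the observed effect, post-hoc power repeats the p-value. For a pre-set difference, it reports precision and leaves out the estimate. In neither form does it show which KOOS differences the data exclude, and section 2.5 names no estimate or interval that would.

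The p-to-power figures need only 15 per arm and a two-sided two-group t comparison. The worked pairs also rest on assumed SDs of change of 10 and 15. Other SDs would move the numbers, but the power would still ignore the estimate. Intervals from the repeated-measures model may be somewhat narrower or wider than those shown, depending on its error term, any baseline adjustment and losses.

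This should be changed before results are seen, but it is a modest point: it concerns how results are interpreted and leaves the validity of the planned test untouched.

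**What to change.** Replace the post-hoc power sentence in section 2.2, and cross-refer to it from section 2.5 (Aim 1), with:

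> For each KOOS subscale, the between-arm difference in change from baseline will be estimated from the repeated-measures model with its 95% CI at 3, 6 and 12 months; 6 and 12 months are the between-arm visits of Hypothesis 1. A non-significant result will be interpreted from its CI and not reported as no difference on the basis of the p-value. Post-hoc power will not be used to evaluate the findings; the observed SD may be used to plan future studies.

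Three months is included because Aim 1, the primary outcome and section 2.5 all cover it.

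Optional, only if the sponsor adopts the 10-point change as a between-arm benchmark, and then at 6 and 12 months:

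- Call a non-significant result inconclusive if its CI includes a 10-point advantage for BMAC and PRP.
- State that a 10-point advantage is excluded if the upper limit is below 10.
- For a result significantly favouring BMAC and PRP, state whether the lower limit is below 10.
- Report each subscale and visit separately, with no overall conclusion across these 5 x 2 = 10 readings.

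The cost is slightly more reporting: 5 subscales x 3 visits = 15 intervals. No patients, visits or data are added and no new power figure is needed. The downside is that some results will have to be called inconclusive.

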The study population will consist of patients who have been diagnosed with KOA (i.e., ICD 10 diagnosis code M17) and have failed initial conservative treatment options. If the patient has bilateral KOA the patient would be excluded unless the patient had only unilateral symptoms. The study will not include patients who have end-stage KOA (i.e., Kellgren-Lawrence grade 4) for which surgical intervention would be more appropriate. Determining a Kellgren-Lawrence grade is a standard of care for diagnosing KOA and is done by reading a standing radiograph of the knee.

The clinic completes an average of approximately 630 office visits per month, 25% of which is related to the care of osteoarthritis. We anticipate that 50% of patients with KOA will satisfy inclusion and exclusion criteria and 80% of eligible patients will be willing to participate in the study. We anticipate enrollment of four patients per month over a maximum enrollment period of 16 months from the start date.

Number of Subjects to be included in the study: 45

We expect that up to 1 of every 3 patients consented will need to be withdrawn prior to the treatment intervention. Withdrawal criteria include use of NSAIDs or corticosteroids within 2 weeks prior to the treatment intervention date, or if a patient's platelet count is found to be <150,000 platelets per microliter of blood or >450,000 platelets per microliter of blood. Withdrawal criteria will be further discussed in section 2.4. We will apply the treatment intervention to only 30 total patients (i.e., n = 15 per treatment group); however, we anticipate consenting up to 45 patients based on possibility of withdrawal from the study. We will discontinue screening and consenting of patients if 30 patients have undergone one of the two treatment interventions.

As attrition following the treatment intervention is only expected to be due to a patient undergoing TKA prior to the 1 year follow-up or due to unforeseen illness, we do not anticipate this having an effect on our population. To further ensure visit compliance, compensation (i.e., a \$25 gift card) will be offered with completion of the 3, 6, and 12 month research follow-up visits.

Proposed Study Start Date: October 1, 2016

Proposed Study End Date: April 1, 2019

Inclusion Criteria:

- 1) Male and female patients 40 to 70 years old
- 2) Diagnosed with KOA based on the American College of Rheumatology criteria including symptomatic reports and radiographic findings

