Patients completing informed consent will be randomized in a 1:1 single-blinded fashion. The randomization allocation schedule will be developed by the research team member performing the statistical analyses and will not be shared with the remainder of the research team. Following the completion of informed consent and collection of baseline information for each patient, the research team member responsible for scheduling the treatment procedure will be made aware of group allocation. This research team member will assign a random number to each patient and independently maintain a key to be able to link the patient to the data collected as well as identify the group membership of each patient. This research team member will not be involved in the collection of 3 month, 6 month, or 12 month study variables. The designated research team member who will collect study variables at 3, 6, and 12 months will remain blinded to group allocation throughout the duration of the study. The primary investigator (i.e., the physician providing the treatment) will not be blinded to group allocation as knowledge of group allocation will be essential to deliver two distinctly different treatment procedures and to provide the participant with an explanation of the clinical procedure prior to initiating the treatment. However, the primary investigator will be unaware of the randomization allocation schedule. Randomization will be blocked to prevent selection and accidental bias while ensuring equal allocation to each treatment group.

Study Treatment/Interventions

After randomization, the patient will be scheduled for the treatment intervention within the next 30 days after the completion of informed consent and baseline procedures. All patients will be restricted from use of NSAIDs or oral corticosteroids for 2 weeks prior to the planned treatment procedure.

At the baseline visit, patients randomized to Group A (BMAC and PRP injections to target knee) will have venous blood sampled by the clinic staff in order to determine the patient's platelet count via a complete blood count (CBC) in the lab based on established procedures. Specifically, the venous blood will be drawn in a lavender-top ethylenediamine tetraacetic acid tube. The sample will be mixed by gently inverting 8 times. The sample will be sent to OhioHealth Laboratory Services and be received within 24 hours at ambient temperature.

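### Blocking is credited with preventing accidental bias but does not balance gender, and gender enters the model only if the arms turn out unequal: a minor point, best settled by adjusting for gender in every analysis.

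*Combined protocol and SAP*

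**What the plan says.** **Allocation (Section 2.4, Randomization).** "Patients completing informed consent will be randomized in a 1:1 single-blinded fashion". The method is blocked: "Randomization will be blocked to prevent selection and accidental bias while ensuring equal allocation to each treatment group". No block size is given, and no stratification factor is named there or elsewhere.

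**Size (Section 2.1).** "We will apply the treatment intervention to only 30 total patients (i.e., n = 15 per treatment group"). Up to 45 may be consented, because up to one in three may be withdrawn before treatment. Sections 2.1 and 2.4 place these withdrawals after randomisation.

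**Gender (Sections 2.3 and 2.5).** For each of KOOS, NPRS and PROMIS, Section 2.5 says that if gender proves unequal between the groups after randomisation, "this statistical method will allow us to control for gender because changes in score will differ by gender". Age and BMI are treated in a similar conditional way. No rule says what counts as unequal. Section 2.3 reports that population reference values for the KOOS subscales "ranged from 61 to 89.5, which also varies by gender".

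**The concern.** The plan asserts that change in score depends on gender, so gender is a factor it has reason to balance or to adjust for. Blocking makes the number of patients per arm equal and keeps the arms in step over the enrolment period. It has no mechanism for equalising the share of women. The protection against accidental bias claimed in Section 2.4 therefore does not extend to gender, and Section 2.5 concedes as much by foreseeing imbalance.

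Two things are at stake. A chance imbalance would shift the unadjusted difference between arms in one small trial. And whether gender is adjusted for at all is left to a judgement made after the groups are seen, with no threshold. Two analysts could look at the same 9 v 6 split and fit different models.

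**Working it through.** **Inputs from the documents:** 30 treated patients, 15 per arm, 1:1 blocked (Sections 2.1, 2.4); up to one third withdrawn between randomisation and treatment (Section 2.1); a 10-point minimal clinically important difference on each KOOS subscale (Sections 1.2, 2.3). The plan gives no figure for gender imbalance to reproduce.

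**Assumptions, not in the documents:** a share of women of 40-70%; a difference between genders of 5-10 KOOS points in mean change; block sizes of 2, 4 or 6, or a random mixture of 2 and 4.

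**1. Chance of a gender gap under blocking alone.** With 15 per arm and a random gender mix, the numbers of women in the arms are independent Binomial(15, q). P(gap of at least m) is the sum of the joint probabilities with |X − Y| ≥ m. One woman is 1/15 = 6.7 points.

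| Share of women q | ≥3 women (20 points) | ≥4 (26.7 points) | ≥5 (33.3 points) |
|---|---|---|---|
| 40% or 60% | 35.1% | 19.1% | 9.2% |
| 50% | 36.2% | 20.0% | 9.9% |
| 70% | 31.8% | 16.1% | 7.1% |

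Simulating the blocked lists gives the same picture: 32-36% for a gap of 20 points or more (blocks of 2, 4 and 6; 50-60% women), and about 34-36% with mixed blocks of 2 and 4 (40-60% women).

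**2. Effect of pre-treatment withdrawal.** Randomise 45, remove one third at random, and compare those treated. A gap of 20 points or more then occurs in about 28-30% of trials without stratification.

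**3. Size of the shift if nothing is adjusted.** Shift = (gender difference in change) × (gap in share of women).
- Gap of 3 of 15: 5 × 0.20 = 1.0 to 10 × 0.20 = 2.0 points.
- Gap of 5 of 15: 5 × 0.333 = 1.7 to 10 × 0.333 = 3.3 points.

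Against the 10-point difference, that is 10-20% for the 3-patient gap and 17-33% for the rarer 5-patient gap.

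**4. Cost of adjusting.** If the gender effect on change is additive, including it in the model removes the shift. The standard error is inflated by 1/√(1 − r²), where r is the correlation between arm and gender.
- 9 v 6 women: r = (9×9 − 6×6)/225 = 0.20; 1/√(1 − 0.04) = 1.02, or 2%.
- 10 v 5 women: r = (10×10 − 5×5)/225 = 0.333; 1/√(1 − 0.111) = 1.06, or 6%.

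**5. What stratifying would add.** With blocks formed within gender, a gap of 20 points or more falls to 0-0.1% if every randomised patient is treated, and to about 7-10% after one-third withdrawal. With blocks of 2 and 4, the randomised arms differ by 0.7 patients on average and by at most 4, before withdrawals.

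**The case against.** The strongest reply is that the plan already deals with the consequence. Section 2.5 provides for gender adjustment in all three analyses, and the shifts in step 3 apply only to an unadjusted comparison. That largely stands, and it is why the point is minor. What remains is that the provision depends on an undefined observation made after randomisation.

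It can also be said that unstratified blocked randomisation is valid and unbiased on average, that blocking does protect against drift in case mix over the enrolment period, and that the plan never promises gender balance in so many words. All of this is right. The claim about accidental bias is too broad, but it is not a flaw that undermines the allocation.

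A reader might infer more than the documents support:
- *That nearly half of such trials would be badly imbalanced.* With exactly 15 women of 30, a gap of 3 or more has probability 46.6%. That is an effect of parity: an odd number of women can only give gaps of 1, 3, 5 and so on. For even counts from 12 to 20 women the probability is 25-27%. With the mix left random it is about one in three.
- *That stratifying abolishes the problem.* It does so only if nobody is withdrawn after randomisation. The plan expects up to a third to be.
- *That Section 2.3 shows change to differ by gender.* It describes score levels in a general population. Only the assertion in Section 2.5 concerns change.

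**Conclusion.** The point holds as a minor one. Blocking does not give the stated protection as far as gender is concerned. A gap of 20 points or more between the arms is an ordinary outcome in a trial of this size (about one in three, or about 28-30% after the expected withdrawals). The rule for responding to it is data-dependent and has no threshold. The likely harm is small: 1-2 KOOS points unadjusted at a 3-patient gap, on an assumed gender effect of 5-10 points, and removable by adjustment for a 2-6% larger standard error at gaps of 3 to 5 women.

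The conclusion rests on an additive gender effect, on an unknown gender mix, and on withdrawals being unrelated to gender and arm. The last is doubtful, since the platelet count that triggers one kind of withdrawal is taken in Group A only. The documents do not support a reading that the randomisation is biased, that gender is ignored, or that the lack of stratification is an error.

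**What to change.** **Section 2.5 (main change).** In the KOOS, NPRS and PROMIS paragraphs, replace the conditional wording with: *Gender will be included in every RM-ANOVA regardless of the balance observed between groups.* Because the plan's premise concerns change, and baseline is one of the repeated measurements, gender should enter with its interaction with time. A main effect alone would adjust the level but not the change. The cost is a few degrees of freedom and no new data, since gender is already collected at baseline.

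**Section 2.4 (wording).** Drop the claim that blocking prevents accidental bias. Say that it keeps group sizes equal and balanced over the enrolment period. This costs nothing.

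**Section 2.4 (optional).** Stratify the blocked list by gender, with randomly varying block sizes. Gender is recorded at baseline, before allocation is released, so two short lists suffice, with no extra patients, visits or staff. There are two downsides. Arm sizes may be slightly unequal, as in step 5. And short blocks within gender, at one site with an unblinded treating physician, may be somewhat easier to predict. If the list is stratified, the main change in Section 2.5 still applies.
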